#### 6.1.1. Medical Devices

Medical devices provided for collecting data in this study are:

- EEG
- Actigraph

### 6.2. Preparation/Handling/Storage/Accountability

ERX-963 (IV ██████████) will be procured by the pharmacy at the clinical sites. IV ██████████ is available as 5 mL or 10 mL vial, containing 0.1 mg/mL of drug. Appropriate volumes for each dose level as summarized in the Table below will be administered over the duration specified.

Dose	Total Volume	Dosing Plan
0.5 mg	5 mL	ERX-963 0.5 mg or placebo will be administered intravenously over 5 minutes.
1.0 mg	10 mL	ERX-963 1 mg or placebo will be administered intravenously over 5 minutes.
2.0 mg	20 mL	ERX-963 2 mg or placebo will be administered intravenously over 15 minutes.

1. The investigator or designee must confirm appropriate temperature conditions have been maintained during transit for all study intervention received and any discrepancies are reported and resolved before use of the study intervention.  
IV ██████ vial should be stored at 25 ° C (77 ° F); excursions permitted to 15 ° to 30 ° C (59 to 86 ° F).
2. Only participants enrolled in the study may receive study intervention and only authorized site staff may supply or administer study intervention. All study intervention must be stored in a secure, environmentally controlled, and monitored (manual or automated) area in accordance with the labeled storage conditions with access limited to the investigator and authorized site staff.
3. The investigator, institution, or the head of the medical institution (where applicable) is responsible for study intervention accountability, reconciliation, and record maintenance (ie, receipt, reconciliation, and final disposition records).
4. Further guidance and information for the final disposition of unused study interventions are provided in the Pharmacy Manual.

### 6.3. Measures to Minimize Bias: Randomization and Blinding

Study using Pre-Coded Randomization provided to site	On the day of dosing in Period 1 participants will be assigned a unique number (randomization number) in ascending numerical order at each study site. The randomization number encodes the participant's assignment to one of the two treatment sequences of the study [Sequence 1: AB and Sequence 2: BA in Cohort 1; Sequence 1: AC and Sequence 2: CA in Cohort 2], according to the randomization schedule generated prior to the study. Each participant will be administered blinded study intervention, labeled with his/her unique randomization number, throughout the study.
Blinded study with unblinded site pharmacist who is dispensing drug	Investigators will remain blinded to each participant's assigned study intervention throughout the course of the study. In order to maintain this blind, an otherwise uninvolved 3rd party will be responsible for the dispensation of all study intervention and will endeavor to ensure that there are no differences in time taken to dispense following randomization.  In case of an emergency, the investigator has the sole responsibility for determining if unblinding of a participant's treatment assignment is warranted. Participant safety must always be the first consideration in making such a determination. If the investigator decides that unblinding is warranted, the investigator should make every effort to contact the sponsor prior to unblinding a participant's treatment assignment unless this could delay emergency treatment of the participant. If a participant's treatment assignment is unblinded, the sponsor must be notified within 24 hours after breaking the blind.  In the event of a Quality Assurance audit, the auditor(s) will be allowed access to unblinded study intervention records at the site(s) to verify that randomization/dispensing has been done accurately.

## 6.4. Study Intervention Compliance

In this study a single dose of the study drug (ERX-963 or placebo) will be administered as a short (5 minute or 15 minute) IV infusion during each of the two treatment periods. The study intervention will be administered by the clinic staff. Deviation(s) from the prescribed dosage regimen should be recorded in the CRF.

## 6.5. Concomitant Therapy

Any medication or vaccine (including over-the-counter or prescription medicines, vitamins, and/or herbal supplements) that the participant was receiving within the last 30 days or is receiving at the time of enrollment or receives during the study must be recorded along with:

- Reason for use
- Dates of administration including start and end dates
- Dosage information including dose and frequency

Lifetime history of medication taken for the treatment of myotonic dystrophy type 1 or sleep will be recorded with the following:

- Reason for use
- Dates of administration including start and end dates
- Dosage information including dose and frequency

The Medical Monitor should be contacted if there are any questions regarding concomitant or prior therapy.

Participants must abstain from taking prescription or nonprescription drugs as outlined in Exclusion Criteria under Prior/Concomitant Medications (Criteria # 10, 11, 12).

### 6.5.1. Rescue Medicine

Not applicable for this protocol.

## 6.6. Dose Modification

This is a single dose study and hence dose modification in cohort 1 is not applicable.

Intravenous [REDACTED] has been used for over two decades for reversal of benzodiazepine induced anesthetic sedation and management of benzodiazepine overdose with an acceptable safety profile. The 1 and 2 mg infusions of ERX-963 (IV [REDACTED] specified in this protocol are lower than the 5 mg maximal dose specified in the FDA approved [REDACTED] product label. Although it is anticipated that the safety profile of single doses of [REDACTED] in participants with DM1 will be similar to the established safety profile of [REDACTED] blinded review of safety (adverse events, safety laboratories and vital signs) will be performed following completion of cohort 1 and prior to initiation of cohort 2. A decision to proceed to cohort 2 with

the planned 2 mg dose, to lower the dose to 1 mg or 0.5 mg, or cease dosing altogether, will be made jointly by the medical monitor and the principal investigators and will be based on the clinical nature adverse events and/or safety laboratory abnormalities observed during cohort 1, their potential for relatedness to active study medication, and the degree of unexpectedness as compared to the existing known [REDACTED] safety profile.

#### **6.7. Intervention at the End of Study**

There will be no study intervention after the end of the study.

## **7. DISCONTINUATION OF STUDY INTERVENTION AND PARTICIPANT DISCONTINUATION/WITHDRAWAL**

### **7.1. Discontinuation of Study Intervention**

In this study single dose of the drug or placebo is administered on two occasions (Study Period 1 and 2). If a decision is made to discontinue the study intervention after Period 1, the participant will not participate further in the study. See the SoA (Section 1.3) for data to be collected at the time of discontinuation and follow-up and for any further evaluations that need to be completed.

#### **7.1.1. Temporary Discontinuation**

Not applicable

#### **7.1.2. Rechallenge**

Not applicable

### **7.2. Participant Discontinuation/Withdrawal from the Study**

A participant may withdraw from the study at any time at his/her own request, or may be withdrawn at any time at the discretion of the investigator for safety, behavioral, compliance, or administrative reasons. This is expected to be uncommon.

Reasons that a participant may be withdrawn include the following:

- the need to take medication that may interfere with study measurements;
- intolerable or unacceptable AEs;
- clinically significant safety laboratory and other test results;
- positive pregnancy test;
- major deviation of study protocol procedures;
- non-compliance of subject with the protocol;
- subject unwilling to proceed and/or consent is withdrawn;
- withdrawal from the study is, in the Investigator's judgment, in the subject's best interest;
- sponsor decision, after discussion with the Investigator;
- study is stopped for any reason.
- At the time of discontinuing from the study, if possible, an early discontinuation visit should be conducted, as shown in the SoA. See SoA (Section 1.3) for data to be collected at the time of study discontinuation and follow-up and for any further evaluations that need to be completed.
- The participant will be permanently discontinued both from the study intervention and from the study at that time.

- If the participant withdraws consent for disclosure of future information, the sponsor may retain and continue to use any data collected before such a withdrawal of consent.
- If a participant withdraws from the study, he/she may request destruction of any samples taken and not tested, and the investigator must document this in the site study records.

### **7.3. Lost to Follow up**

A participant will be considered lost to follow-up if he or she repeatedly fails to return for scheduled visits and is unable to be contacted by the study site.

The following actions must be taken if a participant fails to return to the clinic for a required study visit:

- The site must attempt to contact the participant and reschedule the missed visit as soon as possible and counsel the participant on the importance of maintaining the assigned visit schedule and ascertain whether or not the participant wishes to and/or should continue in the study.
- Before a participant is deemed lost to follow up, the investigator or designee must make every effort to regain contact with the participant (where possible, 3 telephone calls and, if necessary, a certified letter to the participant's last known mailing address or local equivalent methods). These contact attempts should be documented in the participant's medical record.
- Should the participant continue to be unreachable, he/she will be considered to have withdrawn from the study.

Discontinuation of specific sites or of the study as a whole are handled as part of [Section 10.1, Appendix 1](#).

### **7.4 Replacement of Subjects**

Participants who do not complete the crossover portion of the study will be discontinued and replaced with a new participant.

## 8. STUDY ASSESSMENTS AND PROCEDURES

Study procedures and their timing are summarized in the SoA ([Section 1.3](#)). Protocol waivers or exemptions must be discussed with the Expansion medical monitor.

Urgent safety concerns should be discussed with the sponsor immediately upon occurrence or awareness to determine if the participant should continue or discontinue study intervention.

Adherence to the study design requirements, including those specified in the SoA ([Section 1.3](#)), is essential and required for study conduct.

All screening evaluations must be completed and reviewed to confirm that potential participants meet all eligibility criteria. The investigator will maintain a screening log to record details of all participants screened and to confirm eligibility or record reasons for screening failure, as applicable.

Procedures conducted as part of the participant's routine clinical management (eg, blood count) and obtained before signing of the ICF may be utilized for screening or baseline purposes provided the procedures met the protocol-specified criteria and were performed within the time frame defined in the SoA ([Section 1.3](#)).

The estimated amount of planned blood collected from each participant over the duration of the study is described below. Repeat or unscheduled samples may be taken for safety reasons or for technical issues with the samples.

Blood Sample Reason	No. of Samples	Volume per Sample (mL)	Total Volume (mL)
Total PK samples in study	10	6	60
Serum pregnancy test	2	5	10
Clinical laboratory tests (hematology and clinical chemistry)	4	20	80
Hepatitis C Antibody	1	10	10
Biomarker test	1	10	10
Total Estimated Blood Volume During Entire Study (mL)			170

### Screening

During screening, potential participants for the study will be fully informed about the nature of the study and possible AEs. Participants must read and understand the ICF and sign the document after the investigator has answered all questions to the candidate's satisfaction. Further procedures can begin only after the ICF has been signed. Screening will occur within 21 days before the first dose of study drug. Potential study participants will be evaluated for entry into the study according to the stated inclusion and exclusion criteria.

Individuals who are identified during this screening as not eligible for study enrolment should complete the requirements described in [Section 5.4](#).

The following procedures will be obtained or performed to evaluate each participant's general health and qualifications for enrolment into the study:

### Screening Visit 1

- Signed, written informed consent;
- Medical history, including myotonic dystrophy diagnosis history;
- Medication history over the past 30 days, including prescription and non-prescription (over the counter, OTC) medications, herbal medications, vitamins, and minerals. Lifetime history of medication taken for DM1 or sleep;
- MDHI questionnaire to establish baseline disease condition;
- ESS
- Complete physical examination and recording of demographic data including height and weight;
- Vital signs (systolic and diastolic blood pressure [BP], respiration rate and pulse rate);
- Administer the practice outcome measure tests (in the order specified below):
  1. Stanford sleepiness scale [SSS]
  2. Psychomotor vigilance task [PVT]
  3. One-back test
  4. 20 minute rest
- Administer the screening visit outcome measure tests (in the order specified below):
  1. Stanford sleepiness scale [SSS]
  2. Psychomotor vigilance task [PVT]
  3. One-back test
- Other tests to be conducted to verify inclusion and exclusion criteria:
  1. 12-lead ECG and a Pulmonary function test (including Spirometry)
  2. Collection of blood for hematology, clinical chemistry, Hepatitis C antibody and in female subjects of child bearing potential, a serum pregnancy test; An additional plasma sample will be taken from patients who have given consent for future exploration of disease markers;
  3. Urinalysis;
  4. Actigraph will be given for collection of data over 7 consecutive days if ESS is  $\leq 11$ .
  5. Nocturnal Polysomnography (Schedule a visit day for participants who have not taken the test within the last 3 years. If the participant has not had the test performed within 3 years and is treated by and compliant with NIV, then this test is not required for eligibility.)
- Review inclusion and exclusion criteria and restrictions;
- Review of AEs and medication history;

- Instructions and paperwork will be given on when and how to return the actigraph and schedule the visit to conduct polysomnography and/or Period 1.

### Period 1 and Period 2 Evaluation Day

- Allot randomization number (Period 1 only);
- Pre-dose Vital Signs (systolic and diastolic BP, respiration rate and pulse rate within 60 minutes prior to dosing) and brief clinical review;
- Hook up EEG and start recording;
- Place two IV lines on two separate limbs (identify one line for drug administration and the second one for blood sampling);
- Start recording video (if patient consented);
- Administer practice outcome measure tests (order of tests: SSS-PVT-One back; approximate duration of 15 minutes);
- Administer pre-dose baseline outcome measure tests (order of tests: SSS-PVT-One back; approximate duration of 15 minutes) 20 minutes after completion of practice outcome measure test;
- Administration of study intervention (at approximately the same time of day [ $\pm 1$ h] in both Period 1 and 2);
  - **Cohort 1 (1 mg) and Cohort 2 (if selected dose is 0.5 mg or 1 mg):** administer as a 5 minute infusion.
  - **Cohort 2 (if selected dose is 2 mg):** administer as a 15 minute infusion
- Administer outcome measure tests (approximate duration of 15 minutes each) starting at:
  - **Cohort 1 (1 mg) and Cohort 2 (if selected dose is 0.5 mg or 1 mg):** 15 minutes, 45 minutes, 1 hour 15 minutes and 1 hour 45 minutes after the start of IV infusion;
  - **Cohort 2 (if selected dose is 2 mg):** 25 minutes, 55 minutes, 1 hour 25 minutes and 1 hour 55 minutes after the start of IV infusion;
- Obtain blood samples (PK sampling) after conclusion of each set of outcome measure tests to measure plasma [REDACTED] concentrations:
  - **Cohort 1 (1 mg):** at the end of drug administration (5 minutes after the start of dosing) and at approximately 30 minutes, 1 hour, 1 hour 30 minutes and at 2 hours after the start of IV infusion;
  - **Cohort 2 (if selected dose is 0.5 mg or 1 mg):** at the end of drug administration (5 minutes after the start of dosing) and at approximately 30 minutes, 1 hour, 1 hour 30 minutes and at 2 hours after the start of IV infusion;
  - **Cohort 2 (if selected dose is 2 mg):** at the end of drug administration (15 minutes after the start of dosing) and at approximately 40 minutes, 1 hour and 10 minutes, 1 hour 40 minutes and at 2 hours and 10 minutes after the start of IV infusion.
  - The exact time when the blood samples were taken will be recorded.

- End video recording;
- General clinician- and patient-reported questionnaire (CGI-I and PGI-I);
- Vital Signs (systolic and diastolic BP, respiration rate and pulse rate) after completion of all assessments;
- Brief physical examination;
- Obtain blood samples for clinical laboratory tests (hematology and clinical chemistry) at the end of the assessment period;
- Review of AEs and concomitant medications (throughout the day, continuing until the end of the study).

Subjects will be given instructions on when to return to the clinic for Period 2 (approximately 4 to 18 days after Period 1), and for End-of-Study visit (after approximately 4 to 18 days after Period 2).

**End of Study or Early Termination**

The following evaluations will be conducted at the End-of-Study (or early termination) visit, which will be conducted approximately 4 to 18 days after Period 2:

- Physical examination;
- Review of AEs and concomitant medications;
- Vital signs (systolic and diastolic BP, respiration rate and pulse rate);
- Clinical laboratory tests (hematology, urinalysis and clinical chemistry);
- Serum pregnancy test (female subjects of child-bearing potential only).

If a subject discontinues from the study prematurely, every attempt will be made to conduct all these evaluations at the time of discontinuation.

## **8.1. Efficacy Assessments**

### **8.1.1. Vigilance and Sleepiness**

The following battery of outcome measure tests will be administered at times specified in the SoA (Section 1.3), in the order specified below:

#### **1. Stanford Sleepiness Scale (SSS) [1 minute]**

Stanford Sleepiness Scale (SSS) consists of a seven-point scale of equal intervals varying from 1 ("Feeling active and vital; alert; wide awake") to 7 Sleep, ("almost in reverie; sleep onset soon, lost in struggle to remain awake")

#### **2. Psychomotor Vigilance Task (PVT) [5 minutes]**

Psychomotor vigilance task (PVT) is a sustained-attention, reaction-timed task that measures the speed with which subjects respond to a visual stimulus.

#### **3. One-back Task [~4 minutes]**

The One-back task is a memory test in which the participants are presented with a sequence of stimuli, and the task consists of indicating when the current stimulus matches the item presented one step earlier in the sequence.

In addition, after the last outcome measure test, the Clinical Global Impression – Improvement scale (CGI-I) and Patient Global Impression – Improvement Scale (PGI-I) will be recorded in each study period (Guy-1976).

### **8.1.2. Electroencephalogram (EEG)**

Brain activity will be continuously monitored by electroencephalogram (EEG) during the pre-dose and post-dose outcome measures testing. The EEG parameters of interest are theta/alpha and theta/beta spectral ratios, and theta, alpha, and beta percentage power. Additional exploratory parameters may be included in the analysis.

EEG data from the time periods when patients are taking the psychomotor vigilance task will be used to determine the theta/alpha and theta/beta spectral ratios, along with the theta, alpha, and beta percentages. If the PVT test duration does not provide sufficient data to estimate spectral ratios, a longer time period will be used.

## **8.2. Safety Assessments**

Safety will be evaluated based on the occurrence of AEs, clinical laboratory testing (clinical chemistry, urinalysis and hematology), vital signs assessments (systolic and diastolic BP, respiration rate and pulse rate) and physical examinations.

During the study, the Investigator or study site personnel will be responsible for querying and recording AEs and SAEs, as detailed in this section of the protocol. In this study, AEs (including qualifying SAEs) will be reported from the time of signing of the informed consent until the End-of-Study evaluation (approximately 4 to 18 days after Period 2) or early discontinuation. Planned time points for all safety assessments are provided in the SoA ([Section 1.3](#)).

### **8.2.1. Physical Examinations**

A complete physical examination will include, at a minimum, assessment of the Cardiovascular, Respiratory, Gastrointestinal and Neurological systems. Height and weight will also be measured and recorded.

A brief physical examination will include, at a minimum, assessments of the skin, lungs, cardiovascular system, and abdomen (liver and spleen).

Investigators should pay special attention to clinical signs related to previous serious illnesses.

### **8.2.2. Vital Signs**

Vital signs will be measured in a semi-supine position after 5 minutes rest and will include systolic and diastolic blood pressure, respiration rate and pulse rate.

### **8.2.3. Electrocardiograms**

Single 12-lead ECG will be obtained as outlined in the SoA ([Section 1.3](#)) using an ECG machine that automatically calculates the heart rate and measures PR, QRS, and QT intervals.

### **8.2.4. Clinical Safety Laboratory Assessments**

See [Section 10.2, Appendix 2](#) for the list of clinical laboratory tests to be performed and to the SoA ([Section 1.3](#)) for the timing and frequency. Fasting is not required for the clinical laboratory tests.

The investigator must review the laboratory report, document this review, and record any clinically relevant changes occurring during the study in the AE section of the CRF.

The laboratory reports must be filed with the source documents. Clinically significant abnormal laboratory findings are those which are not associated with the underlying disease, unless judged by the investigator to be more severe than expected for the participant's condition.

Laboratory tests with values considered clinically significantly abnormal during participation in the study from the first dose (Period 1) to End of Study visit (or early discontinuation) should be repeated until the values return to normal or to pre-dose levels or are no longer considered clinically significant by the investigator or medical monitor.

### **8.3. Adverse Events and Serious Adverse Events**

The definitions of an AE or SAE can be found in [Section 10.3, Appendix 3](#).

AE will be reported by the participant (or, when appropriate, by a caregiver, surrogate, or the participant's legally authorized representative).

The investigator and any qualified designees are responsible for detecting, documenting, and recording events that meet the definition of an AE or SAE and remain responsible for following up AEs that are serious, considered related to the study intervention or study procedures, or that caused the participant to discontinue the study (see [Section 7](#)).

#### **8.3.1. Time Period and Frequency for Collecting AE and SAE Information**

All SAEs will be collected from the signing of the informed consent form (ICF) until the End-of-Study visit or early discontinuations at the time points specified in the SoA ([Section 1.3](#)).

All AEs will be collected from the signing of the ICF until the End-of-Study visit or early discontinuations at the time points specified in the SoA ([Section 1.3](#)).

All SAEs will be recorded and reported to the sponsor or designee immediately and under no circumstance should this exceed 24 hours, as indicated in [Section 10.3, Appendix 3](#).

The investigator will submit any updated SAE data to the sponsor within 24 hours of it being available.

Investigators are not obligated to actively seek AE or SAE after conclusion of the study participation. However, if the investigator learns of any SAE, including a death, at any time after a participant has been discharged from the study, and he/she considers the event to be reasonably related to the study intervention or study participation, the investigator must promptly notify the sponsor.

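### AE/SAE collection stops at early discontinuation with no minimum time after the dose, so a participant who leaves on a dosing day is not actively followed through the SAP's own treatment-emergent window

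*Protocol*

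**What the plan says.** **End of collection.** Protocol 8.3.1 closes the two windows in the same way: "All SAEs will be collected from the signing of the informed consent form (ICF) until the End-of-Study visit or early discontinuations" and "All AEs will be collected from the signing of the ICF until the End-of-Study visit or early discontinuations". It adds: "Investigators are not obligated to actively seek AE or SAE after conclusion of the study participation". After that, only an SAE that the investigator happens to learn of and considers reasonably related must be notified.

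**What discontinuation means.** Section 7.1: "If a decision is made to discontinue the study intervention after Period 1, the participant will not participate further in the study". Section 7.2: "The participant will be permanently discontinued both from the study intervention and from the study at that time". Intolerable AEs are among the listed withdrawal reasons. For a premature exit, the End of Study or Early Termination part of section 8 says "every attempt will be made to conduct all these evaluations at the time of discontinuation". Those evaluations include AE review, vital signs and laboratory tests.

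**Completers.** Section 8 brings them back 4 to 18 days after Period 1 and again 4 to 18 days after Period 2, with AE review running throughout.

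**Analysis.** The primary endpoint (protocol section 3) is the proportion of participants with AEs, SAEs and drug-related AEs, with no time window named. SAP 12.1 tabulates TEAEs, defined by onset from dosing through Study Day 2 of the period. It counts each patient once per event and once per system organ class. The Safety population is everyone who received at least one dose (protocol 9.3, SAP 4.1).

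**The concern.** Safety is the primary objective, and how long a participant is observed can depend on how well the dose was tolerated. If someone is withdrawn on the dosing day, active collection closes that day. A new event the next day falls inside the SAP's TEAE window but outside active collection, while the person remains in the denominator. A new non-serious event has no stated reporting route, and a new SAE has only the passive route in 8.3.1.

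The tables are not the only use of these data. Cohort 1 adverse events, laboratory results and vital signs feed the blinded review that decides how, and whether, cohort 2 proceeds (protocol 6.6 and 10.1.5). That review is not stated to be limited to TEAEs, and there is no data monitoring committee (9.5.1). A participant withdrawn for poor tolerability could be the least completely observed case in it.

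**Working it through.** **1. The plan's own follow-up figure.** Protocol 1.1 gives a total duration of about 57 days. Summing the maximum intervals: screening 21 + washout 18 + follow-up 18 = 57. It reproduces, and it describes completers only. No minimum post-dose follow-up is given for anyone who stops early.

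**2. Which exits affect the TEAE tables.** The SAP does not say how Study Day is numbered within a period; I take the dosing day as Day 1.

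| Time of exit | Part of TEAE window not actively observed | Effect on TEAE tables |
|---|---|---|
| After Study Day 2 of the period | None | None; later events are lost from collection and listings only |
| Dosing day or Day 2, stopped because of a TEAE | Remainder of the window | None on any-AE; possible on further AE terms, SAEs, severe or drug-related events not yet counted |
| Dosing day or Day 2, stopped for another reason | Remainder of the window | Possible on any category, including any-AE |

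**3. Ceiling from one participant.** At least 6 participants per cohort are expected to complete, and the estimated total of 14 gives 14/2 = 7 per cohort. One participant weighs 1/6 = 16.7 points or 1/7 = 14.3 points. A shift of that size requires the uncounted event to occur with certainty and to be of a type not already counted for that person.

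**4. Expected understatement from one early exit.** Formula: 100 × p × f / n points. Here p is the risk of the event type in the window and f is the share of that risk falling after exit. The documents give neither AE nor dropout rates, so p = 5% to 30% is an assumption. Two choices of f:

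- f equals the fraction of drug remaining 2 hours after dosing, 2^(−120/half-life), using the 40 to 80 minute half-life in protocol 4.2. This gives 2^(−3) = 0.125 and 2^(−1.5) = 0.354.
- f = 1, the whole window missed.

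| n | f = 0.125 to 0.354 | f = 1 |
|---|---|---|
| 6 | 0.1 to 1.8 points | 0.8 to 5.0 points |
| 7 | 0.1 to 1.5 points | 0.7 to 4.3 points |
| 14 | 0.04 to 0.8 points | 0.4 to 2.1 points |

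Worked ends for n = 6: 100 × 0.05 × 0.125 / 6 = 0.1; 100 × 0.30 × 0.354 / 6 = 1.8; 100 × 0.30 × 1 / 6 = 5.0.

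**5. Plausibility of late drug effects.** At 24 hours and an 80-minute half-life, 1440/80 = 18 half-lives have passed, and 2^(−18) = 0.0004% of the drug remains. Most drug-related onsets should therefore be early. That reduces the expected loss but does not make it zero for an exit on the dosing day.

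**6. Do other sections close the gap?** Under 8.3 investigators "remain responsible for following up AEs that are serious, considered related to the study intervention or study procedures", or that caused discontinuation. Sections 8.3.3 and 10.3.3 follow reported events, and 8.2.4 repeats clinically significant abnormal laboratory tests. All of these start from something already known. None requires new events to be looked for after exit.

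**The case against.** A reader might infer that AE proportions are biased low by the contrast between 4 to 18 days for completers and under one day for an early exit, and that this favours the drug. The case against that reading is strong, and most of it stands.

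- The SAP tables stop at Study Day 2 for everyone, so a completer's later days do not enter them.
- A participant stopped because of a TEAE is already in the any-AE numerator and, if the event is judged related, in the drug-related count.
- The documents give no rate showing that early exits are more often on ERX-963. The direction of any bias is inferred.
- The same-day termination laboratory sample does not distort the summaries. Section 8 takes each period's sample at the end of that day's assessments for all participants, and SAP 12.2 summarises those samples.
- Each period is one short infusion, so deciding after Period 1 not to dose again need not mean leaving on the dosing day. Withdrawal is expected to be uncommon (7.2).
- Following a known AE keeps contact open, and that contact may bring a new event to light.

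It could also be said that section 8 times the early termination visit 4 to 18 days after Period 2. That gives nothing to someone who leaves in Period 1, and the closing sentence of the same part puts the evaluations for any premature exit at discontinuation.

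What the objection does not remove is the dosing-day exit. Part of the SAP's own window is then without active collection, by a stated rule.

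**Conclusion.** The gap is real and narrow. Followed as written, 8.3.1 with 7.2 and section 8 can leave a dosing-day exit unobserved for part of the TEAE window while the person still counts in the denominator. SAEs, severe or drug-related events and further AE terms can be understated, and the cohort 1 review can be incomplete. The documents do not support saying that the AE proportions are biased low, or by how much in this trial.

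The 14 to 17 points are the most that one participant with one uncounted event can contribute. For one early exit among 6, the expected understatement is 0.1 to 5.0 points. This rests on assumed risks of 5% to 30%, on the assumed share of risk falling after exit, and on reading the dosing day as Day 1. With no exit before the end of Study Day 2, the effect on the TEAE tables is zero. If the primary proportions were computed on all collected AEs, which the protocol endpoint does not rule out, the unequal follow-up would matter more; the SAP does not plan that.

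The change is worth making because it concerns data collection for the primary endpoint and costs little.

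**What to change.** In protocol 7.1, 7.2, 8, 8.2 and 8.3.1, state that a dosed participant who stops for any reason other than withdrawal of consent keeps AE and SAE collection after the last dose. The minimum should be the SAP's window, through Study Day 2 of the period. The same 4 to 18 days as completers is preferable: it would not change the TEAE tables, but it would make listings and the cohort 1 review equally complete for everyone dosed.

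Keep the termination evaluations at the time of discontinuation, so that they are not lost if the participant does not return, and add the later AE enquiry to them.

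The cost is amendment wording and one further AE enquiry for the few who stop early, with no new type of assessment. The downside is that some of them may not be reachable.
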